Main objective: To test the agreement of standard pinprick (toothpick) sensory recovery testing after spinal anesthesia with the duration of sensory block as determined by the modified device.

Methods and Measures

Design

This is an observational series to determine the agreement of an experimental application of an approved medical device designed to test recovery of sensation from spinal anesthesia, with the customary clinical method of testing recovery from spinal anesthesia.

Subjects selection criteria

- **Inclusion Criteria**
 - Patients 18-75 y/o and scheduled to undergo unilateral primary knee or hip arthroplasty under spinal anesthesia with bupivacaine, ropivacaine or tetracaine will be eligible. The study will be conducted at Wake Forest Baptist Hospital and Davie Medical Center
- **Exclusion Criteria**
 - Exclusions to cold therapy due to medical disease such as Raynaud's disease, Buerger's disease, sickle cell disease, significant peripheral vascular disease (history of limb vascular stents or bypass), hypercoagulable clotting disorders, cold agglutinin disease, history of frostbite of the legs, and neuropathy in the lumbar dermatomes under investigation.
 - Subjects will be excluded if pre-block sensation is abnormal in the L3 dermatome of the non-operative leg, or if spinal anesthesia is not performed or is unsuccessful.
 - Subjects will be excluded if sensation has already returned in the L3 dermatome of the non-operative leg upon arrival to the PACU.
- **Sample Size**
 - Sample size calculations (see analysis below) predict 9 subjects will be sufficient to show equivalence. We will recruit 15 subjects for the study to account for drop-out after enrollment.

Interventions and Interactions

Subjects will be recruited before their surgical date in one of two ways. They may be approached at the conclusion of their preoperative assessment clinic (PAC) appointment to

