After surgery and upon arrival in PACU, if the subject has already recovered sensation at the L3 dermatome (at the "X"), they will be excluded from the study at that time. If they have not recovered sensation, the device pad will be wrapped to the non-operative thigh at the "X" location by a study team member, and an elastic bandage used to secure the cooling pad to the patient. Cycling will begin with 15 min of cold circulation, then 15 minutes off. A PACU nurse who is not aware of the cooling pump activity will test the patient in the lumbar dermatomes (L1 to L4) every 30 minutes per usual practice (the L3 dermatome will be tested adjacent to the cooling pad). The most cephalad level of prick sensation with toothpick stimulus will be recorded on the PACU flowsheet in WakeOne. Cooling pad temperature during pump cycling will be measured with a wireless sensor, and expected to reach approximately 40-50 degrees Fahrenheit when cooling (based on in vitro testing), and return toward body temperature when not cooling; the range will be recorded on the data sheet. Usual PACU discharge criteria will be employed, but it is expected the testing will end when regression of spinal block to L3 is achieved. Study participation will continue until the subject stops the pump cycling, and is expected to continue up to 4 hours.

Outcome Measure(s)

- **Primary Outcome Measure**

Block Recovery Time: Time to resolution of spinal anesthetic (minutes from injection) will be measured in minutes for (i) the device and (ii) standard nursing pinprick testing on the same (non-operative) thigh.

Analytical Plan

Time to resolution of spinal anesthetic will be measured in minutes for (i) our device and (ii) standard nursing pinprick testing on the same (non-operative) thigh. We will test the equivalence of (i) and (ii), where the equivalence region is defined as the difference in (i) and (ii) falling in the interval $[-29, 29]$ minutes. In the sample size calculation, it is assumed that time to spinal resolution has a mean of 140 minutes (standard deviation 29 minutes) such that we are targeting an equivalence region of $[-1, 1]$ standardized units. With type 1 error set to 0.05, we need 9 pairs of observations to achieve 80% power. Calculations were performed using the R package ‘TOSTER’.

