To test equivalence of the measurements in real data, the same procedure of “two one-sided tests” will be employed, with t-tests of the one-sided hypotheses that the null difference is less than -29 minutes or that the null difference is greater than 29 minutes.

Human Subjects Protection

Subject Recruitment Methods

Study team members (Anesthesiology Faculty) will be providing the anesthesia care for patients undergoing hip and knee arthroplasty and routinely review clinical information in the days before surgery to prepare for this care. They will identify eligible patients as a part of this review and let the clinical research staff know of potential subject recruitment. Patients meeting eligibility requirements will be recruited before their surgical date in one of two ways. They may be approached at the conclusion of their preoperative assessment clinic (PAC) appointment to review the study and consent form. If not approached at the PAC visit, they may be contacted by phone prior to the surgical date as described above in “interactions” using a telephone script to introduce the study, review exclusion criteria and determine interest. If interested, patients will have questions answered and later complete a written informed consent in the preoperative holding area on the day of surgery. Patients will NOT be recruited on the day of surgery if they have not already been contacted by phone or seen in person prior to their day of surgery.

Informed Consent

Signed informed consent will be obtained from each subject.

Confidentiality and Privacy

Confidentiality will be protected by collecting only information needed to assess study outcomes, minimizing to the fullest extent possible the collection of any information that could directly identify subjects, and maintaining all study information in a secure manner. To help ensure subject privacy and confidentiality, only a unique study identifier will appear on the data collection form. Any collected patient identifying information corresponding to the unique study identifier will be maintained on a linkage file, store separately from the data. The linkage file will be kept secure, with access limited to designated study personnel. Following data collection

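### The objective is agreement, but the only analysis tests the mean paired difference, and a fixed 140-minute clock that senses nothing would pass it about as often as planned.

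*Combined protocol and SAP*

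**What the plan says.** The main objective (Objectives) is "To test the agreement of standard pinprick (toothpick) sensory recovery testing after spinal anesthesia with the duration of sensory block" found with the modified device. The Design section says the same: "This is an observational series to determine the agreement of an experimental application of an approved medical device". The primary outcome is measured twice in each patient, on the same thigh: "Time to resolution of spinal anesthetic (minutes from injection) will be measured in minutes for (i) the device and (ii) standard nursing pinprick testing".

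The Analytical Plan then sets one criterion: "the equivalence region is defined as the difference in (i) and (ii) falling in the interval $[-29, 29]$ minutes". For sizing, "it is assumed that time to spinal resolution has a mean of 140 minutes (standard deviation 29 minutes"), and from this "we are targeting an equivalence region of $[-1, 1]$ standardized units". With type 1 error 0.05 and 80% power the plan arrives at 9 pairs; 15 subjects are recruited to allow for drop-out. The data are to be analysed by two one-sided tests, namely "t-tests of the one-sided hypotheses that the null difference is less than -29 minutes" and the mirror-image test at +29.

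No other analysis of the two times is specified. The plan mentions no SD of the differences, limits of agreement, concordance measure or proportion of patients within a margin.

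**The concern.** Agreement between two methods of measurement is a question about individual patients: when the device gives a time, how far from the pinprick time is it likely to be? A t-test of the paired difference against ±29 minutes answers a different question, whether the average difference lies inside that interval. A device that reads 50 minutes early in half the patients and 50 minutes late in the other half has no mean bias.

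The spread of the differences does enter the test, but only through the standard error, SD/√n. The tolerated spread therefore grows with the number of patients, which is the wrong direction for an agreement criterion.

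The phrase about the difference falling in the interval could be read as a per-patient requirement. The tests specified, and the calculation that yields 9 pairs, show that it is applied to the mean.

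At stake is the trial's sole objective. A positive test would invite the conclusion that the device agrees with pinprick, when the result is compatible with a device that senses nothing.

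**Working it through.** **Inputs.** From the Analytical Plan: margin ±29 minutes; mean 140 and SD 29 for time to resolution; standardised margin ±1; type 1 error 0.05; power 80%; 9 pairs. From Sample Size: 15 recruited. Assumptions made here: each one-sided test is at 0.05, the true mean difference is 0 in the sizing, and times are normally distributed.

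**1. The plan's own figure.** The normal approximation for a paired two one-sided tests procedure with zero true difference is

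n = (z₀.₉₅ + z₀.₉₀)² / (margin/SD of difference)² = (1.645 + 1.282)² / 1² = 8.56, rounded up to 9.

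This reproduces the stated 9 pairs. It confirms that the test is on the mean difference and that 29 minutes, stated as the SD of a recovery time, was used as the SD of the difference.

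**2. A clock that reads 140 for every patient.** The difference is 140 − T, where T is the pinprick time. Its mean is 140 − 140 = 0 and its SD is SD(T) = 29. These are the sizing inputs, so the clock passes with exactly the power of the device the trial was sized for, at any n.

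| Pairs | Normal approximation | t-tests as specified |
|---|---|---|
| 9 | 0.825 | 0.725 |
| 15 | 0.974 | 0.958 |

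The t-test column comes from numerical integration over the sample SD; simulation of 200,000 trials gave 0.727 and 0.958.

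**3. How well that clock agrees.** Its 95% limits of agreement are ±1.96 × 29 = ±57 minutes. The chance that one patient differs from pinprick by more than 29 minutes is 2 × (1 − Φ(29/29)) = 0.317, or about 32%.

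**4. A variable device unrelated to pinprick.** With the same mean and SD and zero correlation, the SD of the difference is 29 × √2 = 41.0 minutes. It passes with probability 0.28 at 9 pairs and 0.66 at 15.

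**5. Largest observed spread that can still pass.** With an observed mean difference of 0, the tests pass when the sample SD is below 29√n / t₀.₉₅,ₙ₋₁:

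- n = 9: 29 × 3 / 1.860 = 46.8 minutes; limits of agreement ±1.96 × 46.8 = ±92 minutes.
- n = 15: 29 × 3.873 / 1.761 = 63.8 minutes; limits of agreement ±1.96 × 63.8 = ±125 minutes.

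**6. Sensitivity of the clock example.** If the clock is set away from the mean recorded pinprick time, the t-test pass probability falls:

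| Clock off by (min) | 9 pairs | 15 pairs |
|---|---|---|
| 0 | 0.725 | 0.958 |
| 5 | 0.674 | 0.915 |
| 10 | 0.539 | 0.778 |
| 15 | 0.369 | 0.553 |

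If 140 is instead the mean true recovery time and pinprick records the next 30-minute check, the mean recorded time is about 155. A 140-minute clock then passes with probability 0.34 (9 pairs) or 0.52 (15); a clock set at 155 passes with 0.68 or 0.94.

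**The case against.** **Spread is not ignored.** Scattered errors cancel in the mean but inflate the SD, and a large enough SD makes the test fail. At 9 pairs the unrelated device fails 72% of the time, and no data set with a sample SD above 46.8 minutes can pass. This is true, but the limit is indirect and loose, and it rises from 46.8 to 63.8 minutes between 9 and 15 pairs.

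**The ±92 and ±125 figures are extremes.** They need an observed mean difference of exactly 0. If the true SD of the difference were 46.8 at 9 pairs or 63.8 at 15, the test would pass only about 16% or 11% of the time, even without bias. If both methods had SD 29, the true SD of the difference could not exceed 58. These figures should be read as the largest passing sample SD, not as a likely outcome.

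**The clock is a favourable case.** It must be set near the mean recorded pinprick time, and step 6 shows how the pass rate drops otherwise. At 9 pairs its 0.725 is below the stated 80%; it matches the planned power only when both are computed the same way. The 15-pair figures apply only if nobody drops out. These points change the size of the example but not what the test measures.

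**This is a small proof-of-concept series.** That excuses imprecision. It does not excuse an analysis that addresses a different question from the one stated, particularly when a device with no sensing ability can pass.

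**Conclusion.** The concern holds. The objective and the design are stated as agreement, while the only analysis tests whether the mean paired difference lies within ±29 minutes. Under the plan's own mean and SD, a constant 140-minute reading passes with probability 0.725 at 9 pairs and 0.958 at 15, the same as the planned device at equal n, while about 32% of patients differ from pinprick by more than 29 minutes.

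The clock figures assume normal times, that 140 and 29 describe the recorded pinprick time, and that the clock is set at its mean. The underlying flaw does not depend on these assumptions: no criterion in the plan bounds individual disagreement directly. It should be corrected before the data are analysed, because it concerns the sole analysis of the sole objective.

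**What to change.** Make a Bland-Altman analysis the primary agreement analysis in the Analytical Plan. Report the mean difference (device minus pinprick), the SD of the differences, the 95% limits of agreement with confidence intervals, and the number and share of patients whose two times are within 29 minutes. State in advance the limit against which agreement will be judged. Keep the two one-sided tests, but restrict their conclusion to the mean bias being within ±29 minutes.

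The cost is revised wording and a few lines of code on times already being collected; no extra patients are required. The price is precision. The approximate 95% confidence half-width of each limit is t₀.₉₇₅,ₙ₋₁ × SD × √(1/n + 1.96²/(2(n − 1))):

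- n = 9: 2.306 × 0.593 = 1.37 SD, about 40 minutes if the SD is 29.
- n = 15: 2.145 × 0.452 = 0.97 SD, about 28 minutes if the SD is 29.

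The agreement claim from this trial will therefore be modest. If the sponsor wants a firm claim against a stated limit, the sample size would need to be reviewed. The 30-minute pinprick schedule and the device's 15-minute off periods will also widen the limits, even for a device that senses perfectly, and should be considered when the acceptance limit is set.

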Appendix

1. Data collection form

2. Consent form
3. Device information, modification, clinical engineering testing
4. Telephone “script”
